Hypothesis: UPA will decrease bleeding and spotting days in users of the ENG implant with unscheduled bleeding by 30% when compared to placebo as assessed by daily bleeding diaries.

SECONDARY AIMS (SA)

SA1: To evaluate bleeding cessation rates by day 10 following seven days of treatment with either ulipristal acetate or placebo.

SA2: To evaluate participant satisfaction with regards to bleeding pattern after use of ulipristal acetate.

SA3: To evaluate participant satisfaction with regards to medication side effects.

SA4: To evaluate effect, if any, of ulipristal acetate on ovulatory status.

KEY STUDY MEASURES

PRIMARY AIM

1. Daily SMS text message bleeding diaries (Day 1 – Day 30)

SECONDARY AIMS

1. SMS text message bleeding diaries Day 1 – Day 10
2. Phone/in-person survey to assess satisfaction with bleeding pattern at 1, 2, 3, and 4 weeks post-study enrollment
3. Phone/in-person survey to assess satisfaction with medication side effects at 1, 2, 3, and 4 weeks post-study enrollment
4. Serum progesterone levels at baseline and at 1, 2, 3, and 4 weeks post-study enrollment

STUDY DESIGN

The INTERRUPT study is a single-site, double-blinded, randomized, placebo-controlled clinical trial. The total sample size for this study is 104. Of these participants, a subset will undergo weekly venipuncture to assess serum progesterone levels.

RANDOMIZATION SCHEME

A block randomization scheme will be created using a computerized random number generator. In order to keep the research team and participants blinded, assignment will be done by the pharmacy based on this randomization scheme. The pharmacy will make identical UPA and placebo capsules, dispensed as a labeled outpatient prescription after a participant is randomized. The randomization scheme will be generated by a random number table with an allocation ratio of 1:1 in blocks of four with a total of 52 participants in each group for a total sample size of 104.

DESCRIPTION OF METHODS

ULIPRISTAL ACETATE

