All participants will meet with the study coordinate to enroll in the study. Participants in the progesterone subset will also meet with the MA to give a blood sample.

- Try to schedule the enrollment appointment as soon as possible since the eligibility criteria for bothersome bleeding has a small window (*i.e.*, 24 days). If they are unable to enroll within a week, schedule the enrollment appointment and tell them that you will call the day before the appointment to re-screen them for eligibility.
- The enrollment process will take 45 minutes to 1 hour: 45 minutes for the study coordinator visit and 15 minutes for the blood draw.
- Schedule the enrollment visit in Office Tracker in the “DCR Studies” column.
- Send the participant a confirmation email that includes the date and time of their enrollment appointment, directions to the DCR, and a copy of the informed consent document.
- Call the day before the enrollment appointment to confirm.

ENROLLMENT

We will enroll 104 participants overall, 52 participants receiving UPA and 52 receiving placebo. Of these 104 participants, 40 will participate in the progesterone subset, 20 from each intervention group. Participation in this portion of the study will be voluntary and offered to all subjects until maximum enrollment for each group is met.

INCLUSION & EXCLUSION CRITERIA

Inclusion Criteria

- People age 18-45
- Implant placed >90 days and <3 years prior to enrollment
- Greater than 1 bleeding/spotting episode in a 24-day time period
- Willing to be abstinent or use condoms during the study period
- Willing to complete 30-day bleeding diary (via text)
- Ability to send/receive SMS text message
- Willing to be randomized to placebo or ulipristal acetate

Exclusion Criteria

- Non-English speaking
- Implant placed <90 days or >3 years prior to enrollment
- Contraindication to ulipristal acetate
- Inability or unwillingness to comply with medication protocol
- Inability or unwillingness to comply with bleeding diary
- Current breastfeeding

ENROLLMENT PACKET

The following materials are included in the INTERRUPT study packet:

- An orange 9x12 envelope
- 2 informed consent documents
- Prescription order form
- Bleeding diary answer key
- Tax office form
- Gift cards
- Serum Progesterone Standard Clinical Chemistry Form (if participating in the progesterone subset)

Study packets are stored in the top left drawer of the study coordinator's desk.

BASELINE ENROLLMENT

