 - On page 7, all participants will initial “Yes” or “No” based on their preference for being contacted by email.
- When finished, the study coordinator must sign and date both the participant’s copy and their own copy
- The participant signs and dates the consent form
- Give the participant the informed consent form signed only by the coordinator
- The completed consent form with the participant’s signature goes in the enrollment packet

Prescription Order Form

The prescription order form will need to be faxed to the IDS pharmacy in order for the participant to be randomized to receive either UPA or placebo.

- Complete the prescription order form with the participant’s full name, date of birth, and known allergies
- Add the subject ID, which will be written with three digits (e.g., 001)
- Write the correct date
- Fax the prescription order form, along with the signature page of the informed consent document, to the pharmacy
- Put the original prescription order form and the fax confirmation sheet in the study packet.

Contact Information Form

Contact information is obtained at the time of the enrollment for follow-up purposes. We obtain contact information of the participant and one close friend or relative, who will act as an alternate contact if we are unable to get in touch with the participant.

- Enter the information directly into RedCap

Baseline Questionnaire

The study coordinator administers the baseline questionnaire to every participant during the enrollment visit. They will ask the participant to respond to the baseline survey questions based on their experiences to date with their current implant. Below is the process to complete the baseline questionnaire:

- Complete the baseline survey in RedCap
- Open participant’s research file
- Click the “Date” button

- Administer the survey
- At the end of the survey, select “Complete” from the dropdown menu, click “Save”, and tell the participant that they will receive a text message shortly

Verification of Text Message Service

Once the baseline questionnaire is completed, the participant will be automatically sent a text message from the text messaging service (Twilio) to verify that they able to receive the daily bleeding diaries. If they respond to the text message, a check mark will automatically appear next to the link for the “Text Verification” form in RedCap.

Post Randomization Form

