 - If the participant provides their SSN, write it on the form. If they do not, write “Declined” where the SSN would have been written.
- Write each gift card’s number and access code on the top right corner of the form

Wrap-Up

- Remind the participant of the date of their first follow-up and that they will receive their first text message the next morning at 10:00am.
- Thank the participant for participating in the study
- Put completed study packet in the study coordinator’s desk

FOLLOW-UP AND RETENTION

FOLLOW-UP PHONE SURVEYS – STANDARD SUBSET

Follow-up surveys occur at scheduled times during the 30-day study period for each participant. When participants enroll, we will collect contact information which includes the participant's cell phone number, home address, email address, and the phone number of one alternative contact. Participants are contacted by their preferred contact method. If, after 2 attempted calls, the participant cannot be reached or does not call back, email contact is attempted. If the participant has still not responded, their alternate contact provided at enrollment will be called.

Administer Follow-Up Survey

Before beginning the follow-up survey, have the participant confirm their date of birth, verify their mailing address, and tell them the following:

- Everything will remain confidential;
- Participating in the study is voluntary, so if there is a question they do not feel comfortable answering, let the study coordinator know and they can move on; and
- If at any point they have any questions or need something repeated, to please let the study coordinator know.

The study coordinator will ask the participant to respond to the questions based on their experiences over the last week (*i.e.*, since their enrollment appointment or last follow-up survey). Below is the process to complete the weekly follow-up survey:

- Complete the follow-up survey in RedCap
- Open participant's research file
- On the "Participant Information" form:
 - Confirm participant's date of birth and mailing address; make changes as needed
 - Write the date and result of the contact (*e.g.*, completed week 1 follow-up, left message on unidentified voicemail)
- Open the form for the appropriate follow-up survey (*e.g.*, "Follow-Up Survey Week 1")
 - Click the "Date" button
 - Administer the survey
 - At the end of the survey, select "Complete" from the dropdown menu, click "Save"

Schedule Next Follow-Up Survey

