- If any responses are missing, ask the participant to verbally recall her bleeding patterns on the missed days.
- Enter her responses directly into RedCap

Administer Follow-Up Survey

The study coordinator will ask the participant to respond to the questions based on their experiences since their last appointment. Below is the process to complete the weekly follow-up survey:

- Complete the follow-up survey in RedCap
- Open participant's research file
- Open the form for the appropriate follow-up survey (e.g., Follow-Up Survey Week 1)
 - Click the “Date” button
 - Administer the survey
 - At the end of the survey, select “Complete” from the dropdown menu, click “Save”.

Schedule Next Follow-Up Visit

- Schedule their next follow-up appointment within 7 days of their previous follow-up appointment
- Schedule a 15-minute appointment under the “DCR Studies” column in Office Tracker
- Send the participant a confirmation email with the date and time of their next follow-up visit.

If the participant's schedule allows, schedule their Week 4 follow-up appointment on the day or of within a day or two after their last bleeding diary so that they can complete their last follow-up survey

and exit survey at this visit. If their schedule does not allow, schedule a date and time to complete their exit survey over the phone.

Blood Draw

- Escort the participant to the blood draw room.
- Label one Tiger top serum gel tube with “INTERRUPT” and the participant’s study ID #
- Let the MA know the participant is ready for their blood draw.
- Ideally, fill $\frac{1}{4}$ full. Invert tube gently 5 times.
- Complete the Serum Progesterone Standard Clinical Chemistry Form and place in a specimen bag along with the vial
- Take the sample to Core Lab within 2 hours of the draw time
- If you are unable to do so, the sample must be processed in the lab
 - Place the blood tubes in the test tube holder in the lab
 - Allow blood to clot 30 minutes in an upright position at room temperature.
 - Process the Tiger top serum gel tube per the instructions in “Specimen Processing”

Gift Cards

Participants are offered a \$25 gift card after the 1st and 3rd follow-up clinic visits and \$75 in gift cards after the 2nd and 4th follow-up clinic visit for their time and effort at the end of each follow-up visit. Prior to giving the participant their gift cards, complete the Tax Office form with the following information:

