Fifty-two participants will be enrolled per arm, for a total of 104 patients. Previous studies evaluating interventions for implant bleeding have defined a clinically significant difference as a decrease in bleeding/spotting days by 20-40%.^{22,23} Therefore, our effect size will be a 30% decrease in the amount of bleeding/spotting days. The sample size calculation used for this study assumes a standard deviation of 10, an alpha of 0.05, power of 80%, and accounting for 15% drop-out. This standard deviation is based on a previous study that found the standard deviation for the mean number of bleeding/spotting days to be approximately +/- 10 days.²²

STATISTICAL METHODS

Demographics will be presented with descriptive statistics stratified by randomization group. Student t tests, chi-square, and Fisher Exact tests will be used, where appropriate, to compare characteristics of participants receiving ulipristal acetate to those receiving placebo. For the primary outcome, mean number of bleeding days in the 30 days following intervention, if normally distributed, we will use a t-test. If not normally distributed, the Mann-Whitney U test will be employed. These tests will also be employed for our secondary outcomes of bleeding pattern satisfaction, medication side-effect satisfaction, and contraceptive efficacy. For the secondary outcome regarding cessation of bleeding by day 10, as this outcome is dichotomous, we will use a Chi-square test (or Fisher Exact test, if appropriate).

MISSING DATA

Missing data rates and patterns will be assessed twice weekly by the data manager and remedial measures, including re-abstraction of data and retraining of staff, will be used as needed to minimize missing data.

ETHICAL CONSIDERATIONS

INSTITUTIONAL REVIEW BOARD

Washington University School of Medicine in St. Louis, MO, has applied for and been approved through the Washington University School of Medicine's Institutional Review Board (IRB) office (protocol number #201612002).

INFORMED CONSENT

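### The plan lists no pre-dose count of bleeding/spotting days and adjusts for none; recording one would add precision at little cost

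*Combined protocol and SAP*

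**What the plan says.** - **Key Study Measures.** The primary measure is the text diary, Day 1 to Day 30. Bleeding satisfaction is listed as "Phone/in-person survey to assess satisfaction with bleeding pattern at 1, 2, 3, and 4 weeks post-study enrollment". Serum progesterone is the only measure with a listed baseline.
- **Description of Methods; Enrollment (Wrap-Up).** The first dose is taken on Day 0 at the enrollment visit. The first diary text follows the next morning.
- **Inclusion Criteria.** One criterion is "Implant placed >90 days and <3 years prior to enrollment". Another requires more than one bleeding/spotting episode within 24 days.
- **Baseline Questionnaire.** Women are to "respond to the baseline survey questions based on their experiences to date with their current implant".
- **Follow-up surveys.** In the standard subset the coordinator is to "ask the participant to respond to the questions based on their experiences over the last week". In the progesterone subset (40 of 104) women are to "respond to the questions based on their experiences since their last appointment", and the scheduling instruction is "Schedule their next follow-up appointment within 7 days of their previous follow-up appointment".
- **Statistical Methods.** The primary outcome is compared by t-test, or by Mann-Whitney U if not normally distributed. The same tests serve for satisfaction. Other tests "compare characteristics of participants receiving ulipristal acetate to those receiving placebo". No covariate is named for any outcome.

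**The concern.** How much a woman has bled recently is a plausible predictor of how much she will bleed over the next 30 days, yet no listed measure records it in days before treatment. The entry rule does not fill the gap: a woman with two one-day spotting episodes (2 days) and a woman with two ten-day episodes (20 days) can both qualify within 24 days. The baseline survey's general framing covers a long period that differs between women, while the follow-up surveys cover about a week.

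At stake are the precision that a baseline covariate would bring, a listed check that the arms were alike on recent bleeding, and a baseline satisfaction rating that can be read against the weekly ones.

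**Working it through.** **1. Recall periods side by side.** Baseline: 90 days / 7 = about 13 weeks, up to 3 × 52 = 156 weeks. Follow-up: one week in the standard subset; since the last visit, nominally within 7 days, in the progesterone subset. This describes the mismatch and does not measure an effect.

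**2. The plan's sample size.** Inputs from the Sample Size section: SD 10, alpha 0.05, power 80%, drop-out 15%, effect a 30% decrease. The placebo mean and the sidedness of alpha are not given. Assume two-sided alpha and a placebo mean of 20 days, so the difference is 0.30 × 20 = 6 days:

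n per arm = 2 × (1.960 + 0.842)² × 10² / 6² = 43.6, rounded up to 44; 44 / 0.85 = 51.8, rounded up to 52.

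This matches the stated 52. The 20-day mean was chosen because it does so; 18 days would give 64 enrolled per arm and 22 days would give 44. In the other direction, 52 × 0.85 = 44.2, so about 44 completers per arm.

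**3. What a baseline covariate would add.** With r the correlation between the baseline count and the 30-day count, residual variance is multiplied by 1 − r², and the equivalent unadjusted number of completers is 44 / (1 − r²). The documents give no r, so a range is shown. Power is for a 6-day difference with 44 per arm.

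| Assumed r | Variance cut | Residual SD | Equivalent completers per arm | Power |
|---|---|---|---|---|
| 0 | 0% | 10.0 | 44 | 80.4% |
| 0.1 | 1% | 9.95 | 44.4 | 80.7% |
| 0.2 | 4% | 9.80 | 45.8 | 81.9% |
| 0.3 | 9% | 9.54 | 48.4 | 83.9% |
| 0.5 | 25% | 8.66 | 58.7 | 90.1% |

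The variance cut and the equivalent number do not depend on the placebo mean. The power column does.

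**4. Chance imbalance.** If baseline days also had SD 10 (assumed), the standard error of the baseline difference between arms of 52 is 10 × √(2/52) = 1.96 days. A difference of 2 days or more in either direction then has probability about 0.31, and of 3 days or more about 0.13. With equal SDs and r = 0.5, a 3-day imbalance would move the unadjusted estimate by 0.5 × 3 = 1.5 days. The unadjusted standard error already allows for such shifts on average; adjustment would remove them from the particular result.

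**5. Whether the data can be collected in time.** In the listed order of enrollment activities the baseline survey is step 4 and medication is handed out at step 8. The order to the pharmacy goes out at step 2, but the pharmacy holds the assignment and the team and participants are blinded. Answers at step 4 are therefore pre-dose and usable as covariates.

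**The case against.** Four objections have weight.

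- **Nothing planned is biased.** Arms are compared on post-treatment values, no change from baseline in satisfaction is planned, and both arms get the same baseline survey. A reader might infer from the differing recall periods that the satisfaction result is distorted. The documents do not support that.
- **The instruments are not shown.** One framing sentence does not rule out a baseline or screener item on recent bleeding. A reader might conclude that an imbalance could be neither seen nor adjusted for. The documents support only that no such count is listed.
- **A covariate need not share the outcome's recall period.** It only has to predict the outcome. A satisfaction rating framed on the whole time with the implant, if the survey holds one, could serve. The 24-day count proposed here does not match the 30-day outcome either. The case therefore rests on the missing day count more than on the mismatch.
- **The gain is assumed and may be small.** At r = 0.2 it is worth about two completers per arm. Adjustment also means replacing the planned tests, since neither a t-test nor Mann-Whitney U takes a covariate.

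All four stand as limits. It would also be wrong to read every follow-up survey as covering exactly the last week: the progesterone subset answers for the time since the last appointment, which can be longer after a missed visit. The contrast with progesterone should not be pressed for side-effect satisfaction, which has no meaningful pre-dose value.

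What survives is that a plausible predictor of the primary outcome is not listed before treatment and is not used in the analysis, although a survey already given before the first dose could record it.

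**Conclusion.** The point holds as a low-cost improvement, not as a flaw in validity. The loss is precision and a listed balance check on recent bleeding.

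The benefit depends wholly on r. It is close to nothing if r is near zero, a 4% to 9% variance reduction at r = 0.2 to 0.3, and 25% at r = 0.5. The power figures also assume two-sided alpha and a 20-day placebo mean; the imbalance probabilities assume a baseline SD of 10. No gain is computed for satisfaction, because its scale and variability are not given. If the unseen survey already has an item on recent bleeding days, only the analysis needs to change.

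**What to change.** 1. In the baseline survey, before the first dose, record the number of bleeding/spotting days in the last 24 days (the period used in the entry rule). Also ask the follow-up bleeding-satisfaction item with a last-week period. Existing questions on the whole time with the implant can stay as descriptive items.
2. Prespecify as the primary comparison a linear model (ANCOVA) of 30-day bleeding/spotting days on arm and the baseline day count. If the counts are clearly non-normal, use robust standard errors or a rank-based ANCOVA; state in advance which one and how that is decided. Keep the unadjusted test as supportive.
3. Use baseline satisfaction as the covariate for bleeding-pattern satisfaction only, in a model suited to the item's scale. Leave side-effect satisfaction unadjusted.
4. Report the baseline day count by arm with the other characteristics.

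The cost is about one minute of survey time, one covariate in each of two analyses and a change of primary test. Recalled days are less exact than a diary, so the gain may be modest. No extra participants or visits are needed.

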While the participant is completing the text message verification, complete the form through the gift card information. Once the participant has completed the text message verification:

- Complete the tax office form (on paper)
- Schedule the participant’s first follow-up, either in person or over the phone
 - Schedule the first follow-up within 7 days of their baseline enrollment visit
 - For in-person follow-up visits:
 - Schedule a 15-minute appointment under the “DCR Studies” column in Office Tracker
- Explain the bleeding diaries
 - Review bleeding questions the participant will receive by text message
 - Review the process to submit responses to the daily text message

(Blood Draw for Participants in the Progesterone Subset)

We must have a successful blood draw at baseline. If unable to get a blood draw at baseline push enrollment back by one week.

- Escort the participant to the blood draw room.
- Label one Tiger top serum gel tube with “INTERRUPT” and the participant’s study ID #
- Let the MA know the participant is ready for their blood draw.
- Ideally, fill $\frac{3}{4}$ full. Invert tube gently 5 times.
- Complete the Serum Progesterone Standard Clinical Chemistry Form and place in a specimen bag along with the vial
- Take the sample to Core Lab within 2 hours of the draw time
- If you are unable to do so, the sample must be processed in the lab
 - Place the blood tubes in the test tube holder in the lab
 - Allow blood to clot 30 minutes in an upright position at room temperature.
 - Process the Tiger top serum gel tube per the instructions in “Specimen Processing”

Distribution of Medication

Give the participant their 7-day supply of pills and have them take the first dose in the consultation room. Instruct the participation that they will continue to take 1 pill per day for the following 6 days.

Gift Cards

The participant is offered \$50.00 (standard subset)/\$75 (Progesterone subset) in Target gift cards for their time and effort at the end of the enrollment visit. Prior to giving the participant their gift cards, complete the Tax Office form with the following information:

- Write “Enrollment” in the box above the place for the participant’s name
- Participant’s name
- Date gift cards were given
- Participant’s social security number (SSN)
 - The study coordinator must ask the participant if they would like to provide their SSN, however, providing it is voluntary for the participant.

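### SA4 compares progesterone between arms by an unadjusted two-sample test, and the plan does not say how the compulsory baseline value in the 40-woman subset enters the analysis, so precision is likely lost

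*Combined protocol and SAP*

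**What the plan says.** Statistical Methods, under Statistical Considerations, gives the primary outcome a t-test, or a Mann-Whitney U test if the data are not normal. It then adds: "These tests will also be employed for our secondary outcomes of bleeding pattern satisfaction, medication side-effect satisfaction, and contraceptive efficacy". Contraceptive efficacy here is the progesterone outcome of SA4: Investigator Monitoring says that serum progesterone is followed in a subset for that purpose. The section names no regression, analysis of covariance, repeated-measures model or covariate.

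Key Study Measures lists, for the secondary aims, "Serum progesterone levels at baseline and at 1, 2, 3, and 4 weeks post-study enrollment". The enrollment instructions for the progesterone subset say "We must have a successful blood draw at baseline" and postpone enrollment by a week if the draw fails. The order of enrollment activities puts the draw immediately before the medication is handed out. The Venipuncture and Enrollment sections set the subset at 20 women per arm, 40 of the 104.

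The only stated use of baseline characteristics is a descriptive table by arm, together with t, chi-square and Fisher tests "to compare characteristics of participants receiving ulipristal acetate to those receiving placebo".

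**The concern.** The protocol would rather delay a woman's enrollment than go without her pre-dose progesterone, but the analysis plan gives that value no role. Baseline level is the obvious predictor of later level, and with 20 women per arm SA4 has little information to spare. Any variation that baseline could explain stays in the error term.

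The silence also leaves a choice open. The planned tests could be applied to the level at some week, to a summary over weeks, or to change from baseline. These differ in precision, and nothing fixes the choice before the data are seen.

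Significance tests of baseline characteristics do not fill the gap. Under randomisation they test a hypothesis known to be true, and they are no substitute for deciding in advance which baseline values belong in the model.

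**Working it through.** **Is the baseline value usable?** It is drawn after the order goes to the pharmacy but before the first dose, in a double-blind trial, so treatment cannot have affected it. It is compulsory for every woman in the SA4 analysis. It is not available for the other 64 women (104 − 40), so it cannot serve as a covariate for all participants in the primary or satisfaction analyses.

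**The plan's own sample size.** The plan "assumes a standard deviation of 10, an alpha of 0.05, power of 80%, and accounting for 15% drop-out" and a 30% reduction. It does not state the placebo mean or whether the test is two-sided. Assume a two-sided test and a placebo mean of 20 days, so the difference is 6 days:

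n = 2 × (1.960 + 0.842)² × 10² / 6² = 43.6, so 44 per arm; 44 / 0.85 = 51.8, so 52 per arm.

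This matches the stated 104 and uses no covariate. The plan gives no separate calculation for SA4.

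**SA4 with 20 women per arm.** Let r be the correlation between baseline and follow-up on the analysis scale. The documents do not give r; 0.3 to 0.6 is assumed. Take the variance of the follow-up value as 1, with equal variance at baseline.

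- Follow-up value, unadjusted: variance 1
- Change from baseline, unadjusted: variance 2(1 − r)
- Follow-up value adjusted for baseline: variance 1 − r²
- Equivalent women per arm = 20 / variance
- Detectable difference at 80% power, in SD of the follow-up value = 2.802 × √(variance × 2/20)

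| Analysis | r | Variance | Equivalent per arm | Detectable difference (SD) |
|---|---|---|---|---|
| Follow-up, unadjusted | any | 1.00 | 20.0 | 0.89 |
| Change, unadjusted | 0.3 | 1.40 | 14.3 | 1.05 |
| Change, unadjusted | 0.6 | 0.80 | 25.0 | 0.79 |
| Adjusted for baseline | 0.3 | 0.91 | 22.0 | 0.85 |
| Adjusted for baseline | 0.6 | 0.64 | 31.3 | 0.71 |

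Change from baseline beats the plain follow-up value only when 2(1 − r) < 1, that is, when r exceeds 0.5. The adjusted analysis is never worse than change in this calculation, because 2(1 − r) − (1 − r²) = (1 − r)², which is not negative.

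**Cost of adjusting.** These are large-sample figures. Estimating one slope with n per arm multiplies the adjusted variance on average by 1 + 1/(2n − 4) = 1 + 1/36 = 1.028, if baseline is roughly normal on the log scale. With r = 0 the cost is about half a woman per arm (20 / 1.028 = 19.5). Break-even is at r² = 1/37, or r of about 0.16. With this factor, 22.0 and 31.3 become 21.4 and 30.4. One error degree of freedom is also spent, leaving 37 instead of 38.

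**Primary outcome, for scale.** With the assumed 6-day difference, SD 10 and 44 completers per arm, power by the normal approximation is 80.4%. A covariate with correlation ρ to the outcome shrinks the SD to 10√(1 − ρ²). Power is then 80.7% at ρ = 0.1, 81.9% at 0.2 and 83.9% at 0.3, a gain of 0.3 to 3.5 points. The documents give no ρ for any candidate covariate.

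**The case against.** The strongest reply is that nothing here is wrong. In a 1:1 randomised trial the unadjusted tests keep their error rate, and chance imbalance in baseline progesterone is already allowed for in that rate. This stands. A reader might infer that women already raised on Day 0 would bias SA4 or create a false drug effect; the documents do not support that.

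A second reply is that the baseline value may be used after all. It is a listed SA4 measure and the tested quantity is left undefined, so a t-test on change is possible. This stands too: a reader should not conclude that the value goes unused, only that no use is specified. It does not remove the point, since change is the least precise of the three analyses when r is below 0.5.

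Third, the gain rests on an assumed correlation. That is correct, and the true gain could be near zero; but the cost in that case is about 3% of variance.

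Two wider readings are tempting. One is that the primary and satisfaction analyses suffer equally. The documents show no link between implant duration, age or subset and those outcomes. Implant duration appears only as an eligibility window ("Implant placed >90 days and <3 years prior to enrollment"), the satisfaction scale is not described, and the primary diary is a daily text message for everyone. The other is that subset membership, and with it phone or in-person follow-up, may be unbalanced between arms. The plan fixes the subset at 20 per arm, and within SA4 the planned mode is the same for all women.

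**Conclusion.** The point holds for SA4 as a matter of precision and prespecification. The plan specifies an unadjusted test and no role for a baseline value that it makes compulsory in the subset. If r is 0.3 to 0.6, adjustment is worth about 2 to 11 extra women per arm on top of 20. Below about 0.16 it gains nothing and costs very little. The size depends wholly on that assumed correlation and on treating progesterone as a continuous, log-scale outcome, which the named tests suggest but the text does not state.

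The baseline significance tests should go, whatever the correlation. Covariates for the primary outcome are an optional refinement, worth perhaps under 1 to 4 points of power and possibly nothing.

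**What to change.** Before unblinding, amend Statistical Methods as follows.

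1. For SA4, define the outcome as log progesterone at stated post-dose weeks. Analyse it with a linear model (one week or a summary) or a repeated-measures model (weeks 1 to 4), with arm and baseline log progesterone as terms. Include every subset woman with at least one post-dose value. Do not restrict to women not raised on Day 0: that would shrink an already small sample and need a threshold that the documents do not give.
2. Present baseline characteristics by arm descriptively and delete the significance tests.
3. Optionally, name a short covariate list for the primary outcome, for example implant duration (if the exact value is recorded) and subset choice as initialled at consent. Use that choice and not the actual contact mode, because missed visits lead to phone contact after randomisation.

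Items 1 and 2 need wording only: no new visits, samples or participants. The statistical price of item 1 is one degree of freedom and, if the correlation is near zero, a negligible loss of precision. Item 3 needs a check that implant duration was recorded.
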